### **3.2.4. Food Effect Sub-study**

#### **3.2.4.1. Sub-Study Rationale**

As DS-1594b is administered orally, the potential impact of food intake on oral bioavailability is an important consideration. In addition, potential combination agents, such as venetoclax, require administration under fed conditions. Determining the food effect early for DS-1594b will help optimize the prandial condition for DS-1594b dosing. Based on in vitro and animal studies, minimal food effect has been observed thus far.

#### **3.2.4.2. Sub-Study Design**

Following MTD declaration, approximately 6 additional subjects will be enrolled into a food effect sub-study to evaluate the effect of a standard meal on the steady-state PK of DS-1594b.

This sub-study follows a single sequence, crossover design. Subjects will receive oral twice-daily or daily dosing of DS-1594b at a predetermined dose level (at least 50% lower than the RP2D) within 0.5 hours after a standard meal (breakfast and dinner), defined as one containing 600 kcal and 30% fat (~21g fat), from Cycle 1 Day 1 to Cycle 1 Day 8. Subjects should refrain from food and drink, except water, 2 hours before dosing (except for breakfast and dinner) and 2 hours after dosing.

From Cycle 1 Day 9 to Cycle 1 Day 18, subjects will receive the same DS-1594b dose under fasting conditions (i.e. subjects refrain from food and drink, except water, for 2 hours before dosing and for 2 hours after dosing). See Section 5.1.2 (under “food effect sub-study only”) for more details regarding dose administration guidance. On days when PK blood samples will be taken, DS-1594b dosing and meal regimens will be administered at the investigational site. After completion of the sub-study (Cycle 1 Day 18 is the last day of sub-study), subjects will continue with DS-1594b dosing under fasting conditions, same as patients not in sub-study (DS-1594b dosing at least 1 hour before or 2 hours after a meal) starting on Cycle 1 Day 19.

**Note:** The entry criteria will be the same as the preceding cohorts, except for additional concomitant medications restrictions for CYP3A modulators and gastric reducing agents (see Section 4.2). PK sampling timepoints of DS-1594b are outlined in [Table 19](#)[Table 19](#).

Formatted: C-Hyperlink

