#### 2.4.2. Safety Pharmacology and Toxicology

The safety pharmacology parameters were assessed in mice (CNS) and in monkeys (cardiovascular and respiratory systems). DS-1594b was administered orally by gavage in all in vivo studies. In addition, the effect of DS-1594b on the hERG potassium channel current was assessed in vitro. DS-1594b has potent activity on the hERG channel with an  $IC_{50}$  value of 0.3  $\mu$ M. In an in vivo cardiovascular study using telemetered male cynomolgus monkeys, QT and QTc intervals were prolonged following a single administration of DS-1594b at  $\geq 20$  mg/kg in a dose dependent manner. Based on the exposure-response (ER) analysis, the plasma concentration of DS-1594a (free form of DS-1594b) to induce QTc interval prolongation by 10 milliseconds was predicted to be around 1000 ng/mL. No effect on any other cardiovascular or respiratory parameters was noted at doses up to 200 mg/kg. In the 28-day repeated dose toxicity study in monkeys, the QTc interval increased on Days 8 and 22 at  $\geq 60$  mg/kg/day; however, no exacerbation of the increased QTc interval was seen on Day 22 compared to that on Day 8. The anticipated human equivalent dose of the 60mg/kg/day dose in monkeys is approximately 19.2 mg/kg/day.

DS-1594b is highly bound to plasma protein (>97%) in all species. No concentration-dependency was observed across species. Cytochrome P450 (CYP) 3A4 is the primary CYP isoform involved in the metabolism of DS-1594b from the results of experiments using human CYP-expressing microsomes and human liver microsomes. DS-1594b did not inhibit CYP1A2 or CYP2B6 ( $IC_{50} > 50$   $\mu$ M). The  $IC_{50}$  values of DS-1594b were 19.6  $\mu$ M for CYP2C8, 48.4  $\mu$ M for CYP2C9, 2.66  $\mu$ M for CYP2C19, and 27.0  $\mu$ M for CYP2D6 without preincubation and comparable to those with preincubation. In addition, DS-1594b induced time-dependent inhibitory effects on CYP3A.

Results from in vitro studies using Caco-2 cell monolayer systems suggested that DS-1594b is a substrate of efflux transporters. In an exploratory PK study after oral dosing of DS-1594b at 3 mg/kg to rats, AUC increase of DS-1594b was observed by oral pretreatment of elacridar at 50 mg/kg, a P-gp inhibitor which partially inhibits BCRP. These observations indicated that DS-1594b is likely transported by P-gp, and BCRP to a lesser extent.

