### 3.2.4.3. Sub-Study PK Evaluability Criteria

Subjects should meet the following minimum criteria to be considered evaluable for the food effect assessment. PK non-evaluable subjects will be replaced.

- On Cycle 1 Day 8 and Cycle 1 Day 18, subject takes DS-1594b according to the assigned dose.
- Subject has an interpretable PK profile following administration of the assigned dose of DS-1594b on Cycle 1 Day 8 and Cycle 1 Day 18.
- Subject takes DS-1594b under the assigned dose and prandial conditions (first 7 days under fed state, then under fasted state afterwards) for at least 5 consecutive days prior to full PK sampling days on Cycle 1 Day 8 and Cycle 1 Day 18.
- Subject does not vomit within 4 hours after DS-1594b dosing on full PK sampling days.

For toxicity monitoring in each group of the DDI sub-study and food effect sub-study we will use the elimination boundaries in [Table 4](#)[Table 4](#) for BOPN design.

Formatted: C-Hyperlink

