##### 9.4.9.1. Food Effect Sub-Study

The effect of meal on the steady-state PK of DS-1594b will be evaluated in the food effect sub-study when:

- DS-1594b is administered orally twice daily or daily with a standard meal from Cycle 1 Day 1 to Cycle 1 Day 8.
- DS-1594b is administered orally twice daily or daily under fasting condition from Cycle 1 Day 9 to Cycle 1 Day 18.

The analysis will consider the primary PK parameters AUCtau and Cmax of DS-1594b on Cycle 1 Day 8 and Cycle 1 Day 18. A mixed-effects model will be used with treatment period (fed vs. fasting) as a fixed effect and subject as a random effect on log-transformed PK parameter data, and the results will be presented at original scale after back-transformation. The geometric mean of DS-1594b PK parameters (as estimated by the mixed effect model) will be calculated and the geometric mean ratio of DS-1594b PK parameters (Cycle 1 Day 18 relative to Cycle 1 Day 8) will be reported with 90% CIs.

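### The food-effect sub-study doses every subject fed first and fasted second, so any Day 8 to Day 18 change in exposure is counted as a food effect; randomising the order would separate the two at little cost

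*Combined protocol and SAP*

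**What the plan says.** Section 3.2.4.2 states that after MTD declaration "approximately 6 additional subjects will be enrolled into a food effect sub-study", and gives the layout: "This sub-study follows a single sequence, crossover design". Dosing on Days 1 to 8 follows a standard meal. Then: "From Cycle 1 Day 9 to Cycle 1 Day 18, subjects will receive the same DS-1594b dose under fasting conditions". The evaluability criteria in Section 3.2.4.3 fix the same order for everyone ("first 7 days under fed state, then under fasted state afterwards"), as do the administration guidance in Section 5.1.2 and the sampling schedule in Table 19, which puts the full fed profile on Day 8 and the full fasted profile on Day 18.

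For the analysis, Section 9.4.9.1 says: "A mixed-effects model will be used with treatment period (fed vs. fasting) as a fixed effect and subject as a random effect". The result is a "geometric mean ratio of DS-1594b PK parameters (Cycle 1 Day 18 relative to Cycle 1 Day 8) will be reported with 90% CIs". No reverse sequence, separate period term or parallel fasted control is specified, and Section 9.4.2 presents the sub-study results apart from the rest of Phase 1.

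Two statements in Section 2.4.2 bear on whether exposure could change with time: "Cytochrome P450 (CYP) 3A4 is the primary CYP isoform involved in the metabolism of DS-1594b" and "In addition, DS-1594b induced time-dependent inhibitory effects on CYP3A".

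**The concern.** A crossover compares conditions within a subject, but it separates condition from time only if the order varies between subjects. Here it does not. Whatever changes in a subject between Day 8 and Day 18 is attributed to the meal.

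The documents suggest several possible sources of change:

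- The drug is cleared mainly by an enzyme that it inhibits in a time-dependent way, so its own clearance might still be falling after Day 8.
- Subjects have relapsed or refractory acute leukaemia and are in their first weeks of treatment, so disease and organ function may change.
- Some relevant co-medication stays open. H2-antagonists and antacids are allowed with timed separation (Section 5.6.3). P-gp inhibitors are only listed for caution (Table 30), although Section 2.4.2 considers DS-1594b a likely P-gp substrate.

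The result has a use. Section 3.2.4.1 expects it to help choose the prandial condition for DS-1594b and names venetoclax, which is taken with food. DS-1594b is otherwise taken fasted (Section 5.1.2), so the answer bears on Cohort C. Section 3.2.4.1 also reports only a minimal food effect in vitro and in animals, so a modest drift could create or cancel an effect of the size that might be found.

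**Working it through.** The documents give no power or precision figure for this sub-study, so there is none to reproduce.

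**1. Can food and time be separated?** Write the log PK parameter for a subject as subject effect + π (if period 2) + τ (if fasted) + error. In the planned layout the period-2 indicator and the fasted indicator are the same column. With 6 subjects the fixed-effects matrix has 8 columns (6 subjects, period, prandial state) and rank 7. Only the sum is estimable:

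E[log(Day 18/Day 8)] = τ + π.

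The reported ratio is the true fasted/fed ratio multiplied by the drift. With no food effect, a drift of 1.20 is reported as fasted/fed 1.20 (fed/fasted 1/1.20 = 0.83). A true fed/fasted ratio of 1.20 with the same drift is reported as 1.00.

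**2. Is simple accumulation a source of drift?** Section 3.1 estimates the half-life at about 7 to 8 h. At the Day 8 pre-dose time (168 h) the fraction of linear steady state is 1 − 2^(−168/8) = 1 − 2^(−21), above 99.99%. So it is not.

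**3. How much could auto-inhibition add after Day 8?** The documents give no CYP3A turnover rate, degree of inhibition or CYP3A share of clearance, so these are assumptions: enzyme turnover half-life 24 to 96 h; active enzyme at the new steady state (Ess) 25%, 50% or 75%; CYP3A share of clearance (f) 50% or 90%; constant inactivation. Then

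E(t) = Ess + (1 − Ess)·exp(−k·t/Ess), with k = ln 2/turnover half-life, and CL(t) = f·E(t) + 1 − f.

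The Day 18/Day 8 AUC ratio is CL(168 h)/CL(408 h):

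| Turnover half-life | AUC ratio, Day 18/Day 8 |
|---|---|
| 24 h | 1.00 |
| 36 h | 1.000 to 1.004 |
| 72 h | 1.001 to 1.032 |
| 96 h | 1.005 to 1.070 |

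Most of the change comes earlier: over the same inputs, exposure at Day 8 is already 1.11 to 3.08 times the uninhibited value.

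**4. What does a balanced order give?** With 3 subjects per sequence the matrix has rank 8 of 8. The mean period-2-minus-period-1 difference is d1 = π + τ for fed-then-fasted and d2 = π − τ for fasted-then-fed, so (d1 − d2)/2 = τ and the common drift drops out. If carryover into period 2 differs between the sequences by λ, the estimate is τ + λ/2. Freedom from bias therefore rests on λ being negligible.

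**5. What does it cost in precision?** With within-subject log variance s², the planned estimate has variance 2s²/6. The balanced one has (2s²/3 + 2s²/3)/4 = s²/3, which is the same. Only the error degrees of freedom change, from 5 to 4: t(0.95) goes from 2.015 to 2.132, and 2.132/2.015 = 1.058. The within-subject CV is not given. Using half-width t·s·√(2/6) and s = √ln(1 + CV²):

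| Assumed CV | 90% CI factors, planned | 90% CI factors, 3+3 |
|---|---|---|
| 20% | 0.79 to 1.26 | 0.78 to 1.28 |
| 30% | 0.71 to 1.41 | 0.70 to 1.44 |
| 50% | 0.58 to 1.73 | 0.56 to 1.79 |

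**The case against.** The strongest reply is that the plan already limits drift and that what remains is small. Both profiles are taken at the same dose, at intended steady state and after at least 5 consecutive days in the assigned prandial state (Section 3.2.4.3). Section 4.2 excludes subjects who cannot stop strong or moderate CYP3A modulators or proton pump inhibitors. The modelled 0 to 7% lies well inside a 90% CI of 0.71 to 1.41. The ratio is a descriptive secondary PK result with no decision margin attached. Fasted escalation subjects are sampled on Days 8 and 15 (Tables 14 and 15), and Section 9.4.9 plans a population PK model; either could inform a time trend.

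Much of this stands, and it limits the weight of the point. It does not remove the aliasing. Imprecision shows in the interval; this bias does not. Neither the escalation data nor the population model is specified for this purpose. The escalation subjects may also be on other doses, since the sub-study dose is at least 50% below the RP2D.

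A fair objection to the remedy is that auto-inhibition depends on exposure. If food alters exposure and inhibition is slow to settle, period 1 could carry into period 2 differently in the two sequences. The estimated half-life and the 5-day minimum make direct drug carryover unlikely, but the assumption has to be stated.

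A reader might also want to use the Day 8 and Day 15 escalation data to correct the azole sub-study, where the inhibitor has to be added second. The data do not support that. Day 15 sampling is pre-dose and 2, 4, 6 and 8 h only. It lacks the 0.5, 1 and 3 h samples and, for BID dosing, the 12 h sample. It also ends before Day 18 and well before Cycle 2 Day 10, and the doses may differ.

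**Conclusion.** Food and time are fully aliased, both in the sub-study's design and in its planned model. That follows from the text and needs no assumption. A drift of x% in exposure between Day 8 and Day 18 shifts the reported fasted/fed ratio by x%.

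Whether there is any drift is unknown: the bias is possible, not demonstrated. For auto-inhibition alone the estimate is about 0 to 7%, on enzyme-turnover inputs that do not come from the documents. Changes in disease, organ function and unrestricted co-medication are not quantified.

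A reader might infer from Section 2.4.2 that clearance falls substantially after Day 8. Falls of 10%, 20% or 30% would give ratios of 1/0.90 = 1.11, 1/0.80 = 1.25 or 1/0.70 = 1.43. The documents do not support such falls. They report time-dependent inhibition among the in vitro enzyme results and give no size or time course in patients, and all three ratios exceed the modelled range.

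The point affects the interpretation of a secondary PK objective, not the primary endpoints. It is worth acting on because the remedy is cheap and the documents give no reason for the fixed order.

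**What to change.** - Randomise the roughly 6 subjects 1:1 to fed-then-fasted or fasted-then-fed, keeping the same days, dose and PK sampling. Each replacement for a non-evaluable subject takes the sequence of the subject replaced.
- Fit prandial state and period as separate fixed effects, with subject random, on the log scale.
- Define the reported ratio by prandial state instead of by day, and state its direction. Table 2 words the objective as fed compared with fasted, whereas the Day 18/Day 8 ratio is fasted over fed.
- State the assumption of no carryover into the Day 8 and Day 18 profiles.
- Leave the azole sub-study without a drift-adjusted ratio.

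The cost is a short randomisation list, one error degree of freedom (90% CI about 6% wider on the log scale at N = 6), and Day 1 single-dose parameters split into about 3 fed and 3 fasted. No subjects, visits or PK samples are added. The text that sets the fed-then-fasted order in Sections 3.2.4.2, 3.2.4.3, 5.1.2 and 9.4.9.1 and in Table 19 needs matching edits, and Section 3's description of Phase 1 as non-randomised needs an exception. Section 8.4.1 ties meal records to Days 1 and 8, so it should also cover fed dosing on Day 18.

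In the same edit, reconcile the day of the second food-effect profile: Sections 8.4 and 9.4.9 give Cycle 1 Day 15, while Sections 3.2.4.3 and 9.4.9.1 and Table 19 give Day 18.

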### 3.2.4.3. Sub-Study PK Evaluability Criteria

Subjects should meet the following minimum criteria to be considered evaluable for the food effect assessment. PK non-evaluable subjects will be replaced.

- On Cycle 1 Day 8 and Cycle 1 Day 18, subject takes DS-1594b according to the assigned dose.
- Subject has an interpretable PK profile following administration of the assigned dose of DS-1594b on Cycle 1 Day 8 and Cycle 1 Day 18.
- Subject takes DS-1594b under the assigned dose and prandial conditions (first 7 days under fed state, then under fasted state afterwards) for at least 5 consecutive days prior to full PK sampling days on Cycle 1 Day 8 and Cycle 1 Day 18.
- Subject does not vomit within 4 hours after DS-1594b dosing on full PK sampling days.

For toxicity monitoring in each group of the DDI sub-study and food effect sub-study we will use the elimination boundaries in [Table 4](#)[Table 4](#) for BOPN design.

Formatted: C-Hyperlink

## 3.3. Phase 2 Design

Enrollment in Phase 2 will start once the RP2D has been determined in Phase 1. This Phase 2 study will have four cohorts:

- Cohort A: DS-1594b monotherapy for R/R AML with MLL-r,
- Cohort B: DS-1594b monotherapy for R/R AML with NPM1m,
- Cohort C: DS-1594b in combination with azacitidine and venetoclax for R/R AML with NPM1m or MLLr
- Cohort D: DS-1594b in combination of mini-HCVD for R/R ALL with MLLr

Subjects enrolled in Cohorts A and B will receive the RP2D dose of DS-1594b determined in Phase 1. Cohorts C and D will enroll an initial 6 subjects in a safety run-in at one dose level below the RP2D (Dose level 0) with DS-1594b dose titration as specified below.

Cohorts A and B (single agent cohorts) will enroll a maximum of 26 subjects, and Cohorts C and D (combination cohorts) will enroll a maximum of 32 subjects, to allow reasonable determination of CRc within 3 months of therapy initiation.

For the combination cohorts (C & D) there will be a safety-run in evaluation with pre-defined toxicity stopping rules to be implemented for early DLT evaluation as per following plan:

- Safety run-in evaluation by the Safety Review Committee of the first 6 subjects in cohorts C and D will occur after 6 subjects have completed at least one cycle of treatment (or at least 28 days from the first day of treatment).
- Enrollment will be paused while the first 6 subjects are evaluated for safety. Each combination cohort will be evaluated independently.
  - If  $\leq 1$  of the 6 subjects experiences DLT in the first cycle of treatment, the treatment combination will be considered as safe and the DS-1594b dose can be escalated to the RP2D (Dose level 1) for the treatment of the next 6 patients (repeat the safety run-in evaluation). If the RP2D (Dose level 1) is considered safe, continue enrollment of an additional 20 subjects at the RP2D (i.e. total subjects treated at the RP2D will be 26 subjects; total cohort size will be 32 subjects). If  $\geq 2$  of 6 subjects at the RP2D experiences DLT in the first cycle of treatment, de-escalate and continue enrollment of an additional 20 subjects at Dose Level 0.
  - If  $\geq 2$  of 6 subjects have DLTs in the first cycle of treatment at Dose Level 0, then an additional 6 subjects will enroll at a next lower dose level to be determined by the Principal Investigator and Safety Review Committee after reviewing the safety, efficacy, and PD data from the first 6 subjects enrolled ([Table 6](#)[Table 6](#), [Table 7](#)[Table 7](#)). If  $\leq 1$  of the additional 6 subjects treated at the lower dose level experience DLTs, this treatment combination will be considered as safe and continue to enroll to a total of 26 subjects (i.e. an additional 20 subjects at the lower dose level; total cohort enrollment of 32 subjects). If  $\geq 2$  of these 6 additional subjects experienced DLTs, then enrollment at the current dose level will be closed.
- Subjects must receive at least 75% of the doses of DS-1594b, azacitidine (Phase 2 only), venetoclax (Phase 2 only), or miniHCVD (Phase 2) during the first 28 days on trial (i.e. during Cycle 1) to be considered evaluable during the DLT evaluation period. Any subjects who are not evaluable for DLT in either cohort during the safety-run in period will be replaced for the assessment of DLT rate. This will allow for early identification of significant toxicities and early stoppage in the combination cohorts.
- The Safety Review Committee (SRC) will meet when there are enough DLT-evaluable subjects to review in each cohort who have completed the DLT evaluation period. The SRC will review the DLT data, other AE data, and available PK/PD, ECG, and laboratory data before proceeding to expansion of each of the cohorts to enroll the additional 20 subjects.

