  - Grade 3 or 4 Differentiation Syndrome which improves to  $\leq$  Grade 1 within 7 days of the start date of  $\geq$  Grade 3 Differentiation Syndrome and which is not associated with end-organ damage. Note: Grade 1 is mild, Grade 2 is moderate, Grade 3 is serious, and Grade 4 is life-threatening.

- CTCAE Grade 3 QTcF prolongation (based on the average of 3 triplicate 12-lead readings or Holter monitor reading)
- Results in dose-reduction or discontinuation of therapy
- Any treatment-related death;
- Subjects not considered evaluable due to insufficient dosing (at least 75% of doses of study drugs) and who do not develop a toxicity that is considered a DLT will be replaced. These subjects may continue therapy on trial after discussion with the Principal Investigator if they are having clinical benefit and the reasons for continuation and potential benefit/risk profile for the subject must be clearly documented in the medical records.
- **Phase 2 only:** For subjects in venetoclax- or Mini-HCVD-containing regimens (cohorts C and D) who do not receive venetoclax or Mini-HCVD on Day 1 due to logistical and/or financial reasons, the DLT period will be extended to 28 days from the first dose of venetoclax or Mini-HCVD. For evaluation of hematologic-related DLT, the DLT evaluation period will be 42 days from the first dose of venetoclax or Mini-HCVD.
- Subjects must receive at least 75% of the doses of DS-1594b, azacitidine (Phase 2 only), venetoclax (Phase 2 only), or miniHCVD (Phase 2) during the first 28 days on trial (i.e. during Cycle 1) to be considered evaluable during the DLT evaluation period. Subjects who receive less than these planned number of doses of each drug during the first 28 days on trial will not be considered evaluable during the DLT evaluation period. However, if such subjects develop a toxicity that would normally be considered a DLT this will still be captured as a DLT. Any toxicity that meets the criteria for DLT during the first 28 days of trial in a subject who has received at least one dose of trial medication will constitute a DLT.
- For subjects who discontinue therapy, the reason for treatment discontinuation will be documented.
- Dose modifications other than the ones mentioned above can be considered after discussion with the PI and proper documentation of the rationale.

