#### **Venetoclax:**

a During Cycle 1, venetoclax administered orally will be dose escalated daily to the goal dose of 400mg daily. Subjects will receive 100mg on Day 1, 200mg on Day 2 and 400mg on Day 3 and onwards, or adjusted ramp up per drug label if on concomitant azoles. The goal is to administer 28 days of venetoclax in Cycle 1 unless marrow remission with concomitant marrow hypocellularity and/or myelosuppression is confirmed earlier than Cycle 1 Day 28. In this case the venetoclax may be stopped earlier to avoid venetoclax related myelosuppression or further marrow hypo/aplasia after discussion and approval from the PI. Venetoclax dose ramp-up as described in Section 5.4.2

b If a bone marrow remission (<5% blasts) or aplasia/hypoplasia (<10% cellularity or insufficient sample) is not confirmed on the Day 21 bone marrow, subjects should continue venetoclax until day 28 and have a repeat bone marrow on Day 28 (+/- 5 days). If the Day 28 bone marrow shows ≥ 5% blasts proceed with cycle 2 if this is in the best interest of the subject (those with C1D28

bone marrow  $\geq 5\%$  are allowed to receive 21 days of venetoclax in Cycle 2 after discussion and approval from the PI). If the Day 28 bone marrow shows  $< 5\%$  blasts or aplasia/hypoplasia follow steps outlined in the Azacitidine administration information “a” and “b” below.

c Venetoclax will be administered orally daily on Days 1 to 28 of the first cycle; and may be reduced to Venetoclax Days 1 to 21 or less for subsequent cycles after PI approval.

d Results from published in vitro and clinical DDI studies revealed a need to modify the dose of venetoclax when it is co-administered with moderate or strong CYP3A inhibitors or P-gp inhibitors (VENCLEXTA® USPI). Based on in vitro assessment, DS-1594b has the potential to inhibit CYP3A-mediated metabolism and P-gp mediated transport of venetoclax in vivo. Thus, dose level(s) of venetoclax should be recommended by the SRC based on emerging DS-1594b PK and safety data, and the dose level of venetoclax and DS-1594b may be adjusted after review of the data collected during the safety run-in evaluation.

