#### **Azacitidine:**

Azacitidine (75 mg/m^2/day) will be administered subcutaneously (SQ) or intravenously (IV) for the first 7 days of every cycle. Azacitidine may be given in a 5on - 2off - 2on or 4on - 2off - 3 on or other similar modified schedule if the subject is not able to get weekend infusions. Azacitidine is administered in the clinic or chemotherapy administration area. Both SQ and IV forms of administration are FDA approved and are allowed and considered interchangeable. Subjects may start receiving azacitidine by one route and change to the other, and administration schedules from one schedule and change to the other at any time as needed based on subject and/or physician preference.

- In Cycle 1, subjects should undergo a bone marrow aspiration and biopsy on Day 21 (+/- 4 days). Subjects who achieve a confirmed marrow remission (i.e. bone marrow blasts  $< 5\%$  by morphology) or marrow aplasia/hypoplasia ( $\leq 10\%$  cellularity or insufficient sample) may discontinue venetoclax for the remainder of the cycle and be monitored for count recovery.
  - If the Day 21 bone marrow shows  $< 5\%$  blasts, the venetoclax may be held, and consider delaying cycle 2 till ANC  $> 0.5 \times 10^9/L$  and platelets are  $> 30 \times 10^9/L$  without platelet transfusion support for  $> 5$  days.
  - If the Day 21 bone marrow shows aplasia/hypoplasia ( $\leq 10\%$  cellularity or insufficient sample), the venetoclax may be held on Day 21 to avoid venetoclax related myelosuppression or further marrow hypo/aplasia, and a repeat bone marrow should be performed on Day 28 (+/- 4 days) to confirm response and MRD assessment. If the Day 28 bone marrow shows  $\geq 5\%$  blasts, proceed with Cycle 2 if this is in the best interest of the subject (those with C1D28 bone marrow  $\geq 5\%$  are allowed to receive 21 days of venetoclax in Cycle 2). If the Day 28 bone marrow shows  $< 5\%$  blasts, the venetoclax may be continued to be held, and consider delaying cycle 2 till ANC  $> 0.5 \times 10^9/L$  and platelets are  $> 30 \times 10^9/L$  without platelet transfusion support for  $> 5$  days. If the Day 28 bone marrow shows persistent aplasia/hypoplasia ( $\leq 10\%$  cellularity or insufficient sample) venetoclax may be held to avoid venetoclax related myelosuppression or further

marrow hypo/aplasia and consider repeating a bone marrow in approximately 10-14 days.

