- If a subject achieves CRi or has a morphologically leukemia free bone marrow after completion of a cycle, DS-1594b may be interrupted from Day 21 for up to 14 days or until recovery of  $ANC \geq 0.5 \times 10^9/L$ . The next cycle administration will also be delayed until  $ANC \geq 0.5 \times 10^9/L$ . If DS-1594b is interrupted then the next cycle administration of chemotherapy will also be delayed. The next cycle with both DS-1594b and chemotherapy will resume on the same day after the interruption.
- If a subject presents with new onset Grade 4 neutropenia for more than 1 week during subsequent cycles, unless it is thought to be due to the underlying disease, DS-1594b dosing may be interrupted until ANC recovery to  $>0.5 \times 10^9/L$  in consultation with the study PI. DS-1594b may be re-initiated at a lower dose per discussion between the treating physician and the study PI.
- Other modifications of drug schedules may be implemented if judged to be in the best clinical interest of the subject after discussion with PI or at the discretion of the treating physician. This includes delays in chemotherapy cycles because of persistent myelosuppression, other side effects, subject request, or other reasons. Missed doses of DS-1594b do not need to be made up.
- Dose reductions exceeding those above or in other agents, e.g., leucovorin, antibiotics, antiemetics, etc., are allowed after discussion with the Principal Investigator.

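### In Cohort C, a protocol-permitted venetoclax hold can make a DLT-free subject non-evaluable while subjects with a DLT are always kept, which inflates the run-in DLT rate

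*Combined protocol and SAP*

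**What the plan says.** **Evaluability.** Section 3.3 opens its rule with "Subjects must receive at least 75% of the doses of DS-1594b, azacitidine (Phase 2 only), venetoclax (Phase 2 only" and applies it to the first 28 days. Section 3.2.2 repeats it and adds: "Subjects who receive less than these planned number of doses of each drug during the first 28 days on trial will not be considered evaluable". I read this drug by drug, so that a shortfall in venetoclax alone is enough.

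**Asymmetry.** Section 3.3: "Any subjects who are not evaluable for DLT in either cohort during the safety-run in period will be replaced". Section 3.2.2, on subjects below the threshold: "However, if such subjects develop a toxicity that would normally be considered a DLT this will still be captured as a DLT".

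**Venetoclax in Cohort C.** Note c to Table 6 (Section 5.4.1): "Venetoclax will be administered orally daily on Days 1 to 28 of the first cycle". The first marrow is due on Day 21 ± 4 days. If it shows remission, or aplasia or hypoplasia, venetoclax may be stopped for the rest of the cycle. For aplasia or hypoplasia, "the venetoclax may be held on Day 21 to avoid venetoclax related myelosuppression". DS-1594b continues as scheduled during such a hold.

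**Run-in decision (Section 3.3).** At most one DLT in six passes a dose level; two or more fail it. The rule is applied at Dose Level 0 and again at the RP2D, or at a lower level if Dose Level 0 fails.

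Nowhere do the documents say how doses withheld under the marrow provisions count toward the 75%.

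**The concern.** The marrow provisions apply to subjects whose leukemia has cleared or whose marrow is hypocellular. If following those provisions takes such a subject below 21 doses, the subject leaves the run-in denominator when DLT-free and stays when there was a DLT. Selection then depends on the outcome being measured.

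The run-in decides the dose with six subjects, so small shifts matter. Two DLTs at the RP2D send the remaining 20 subjects to Dose Level 0, and the cohort's efficacy estimate would then rest mainly on the lower dose. Two DLTs at the lower level close enrollment there. Replacement also uses up subjects.

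**Working it through.** **The plan's own count.** Section 9.4.1.3 gives the threshold for twice-daily DS-1594b in dose escalation as 42 of 56 doses: 0.75 × 56 = 42, which reproduces. The same rule on 28 daily venetoclax doses gives 0.75 × 28 = 21.

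**Where the threshold falls** (start on Day 1, no dose lost):

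| Last venetoclax dose | Share of 28 | At least 75%? |
|---|---|---|
| Day 17 (earliest marrow day) | 17/28 = 60.7% | No |
| Day 20 | 20/28 = 71.4% | No |
| Day 21 | 21/28 = 75.0% | Yes, exactly |
| Day 25 (latest marrow day) | 25/28 = 89.3% | Yes |

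The threshold falls on the nominal marrow day, and Section 5.4.1 does not say whether the dose on the day of the hold is taken. There is also no slack at Day 21: one earlier dose lost gives 20/28. The protocol foresees such losses. A missed or vomited dose is not compensated by a larger next dose (5.4.2). Interruptions of up to 72 hours for laboratory tumor lysis are allowed (5.4.1, 6.4). The first dose waits until the white count is low enough (5.4.1). With a Day 3 start, dosing must run to Day 23 to reach 21 doses. Section 3.2.2 extends the DLT period for a late start only when the reason is logistical or financial.

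**Effect on the run-in.** Let p be the true DLT rate among all treated subjects and h the share of DLT-free subjects who fall below 21 doses and are replaced. Every subject with a DLT fills one of the six places, as in the dose-escalation set of 9.4.1.3. Then

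- rate among evaluable subjects: q = p / [p + (1 − p)(1 − h)]
- chance of failing: P(≥2 of 6) = 1 − (1 − q)^6 − 6q(1 − q)^5
- expected enrollment for six evaluable: 6 / [p + (1 − p)(1 − h)]

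Example, p = 0.20 and h = 0.25: q = 0.20 / (0.20 + 0.80 × 0.75) = 0.25. P = 1 − 0.1780 − 0.3560 = 0.466. Enrollment = 6 / 0.80 = 7.5.

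| p | h | q | P(≥2 of 6) | Expected enrollment |
|---|---|---|---|---|
| 0.20 | 0 | 0.200 | 34.5% | 6.0 |
| 0.20 | 10% | 0.217 | 38.7% | 6.5 |
| 0.20 | 25% | 0.250 | 46.6% | 7.5 |
| 0.20 | 40% | 0.294 | 56.7% | 8.8 |
| 0.10 | 0 | 0.100 | 11.4% | 6.0 |
| 0.10 | 10% | 0.110 | 13.4% | 6.6 |
| 0.10 | 25% | 0.129 | 17.5% | 7.7 |

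The value of h is an assumption. For reference only, 25% and 40% are the historical and target response rates in Section 9.3. Those are three-month rates, not rates of holding venetoclax before the 21st dose.

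**The case against.** **A Day 21 hold is not disqualifying in itself.** A reader might infer that it always is. It is not: a subject who started on Day 1, missed nothing and took the Day 21 dose has exactly 75% and is evaluable. A hold after a later marrow in the window leaves more doses. This stands, and it limits the concern to last doses by Day 20, or by Day 21 with a loss or late start.

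**The plan may already be conditional.** Section 3.2.2 speaks of the planned number of doses, and note a to Table 6 makes 28 days a goal that yields to an earlier confirmed remission with hypocellularity or myelosuppression. On that reading a permitted stop shortens the plan. It is arguable, but note c gives Days 1 to 28 without condition and 3.2.2 does not adopt the conditional reading.

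**The size is not known.** The holds are permissive and h is nowhere given. This stands. If few subjects fall short, the effect is small.

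**The error is cautious.** It favors de-escalation in a first combination run-in. Replaced subjects remain in the safety set, and the Safety Review Committee also sees other adverse event data. In addition, a hematologic DLT requires cytopenia lasting to Day 42 without residual leukemia, whereas the run-in review may take place after 28 days. DLTs not yet observed in responders could offset part of the inflation. All of this bears on severity; it does not remove the selection.

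**Cohort D.** A reader might extend the point to Cohort D, where "DS-1594b may be interrupted from Day 21 for up to 14 days". That provision applies after a completed cycle. The first scheduled marrow is at the end of Cycle 1 (5.5.1), Day 28 ± 4 (8.3), so Day 24 at the earliest, when 24/28 = 85.7% of dosing days have passed. Only an unscheduled earlier marrow could cause a problem.

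**The Section 9.3 toxicity rule.** A reader might also infer that this rule is biased in the same way. Section 9.3 does not say that it uses the 75% criterion, and the DLT Evaluable Set in 9.4.1.3 is confined to dose escalation. An effect there is not established.

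**Conclusion.** The point holds for venetoclax in the Cohort C run-in. As written, the rule can drop DLT-free subjects whose venetoclax was held in line with Section 5.4.1, while it retains every subject with a DLT. For any h above zero the evaluable-set DLT rate exceeds the all-treated rate.

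At a true rate of 20%, failure of a six-subject run-in moves from 34.5% to between 38.7% and 56.7% for h from 10% to 40%. At 10%, it moves from 11.4% to 17.5% for h = 25%. These figures rest on the assumed h, on reading the 75% drug by drug, and on counting all 28 days as planned; they ignore any offset from late hematologic DLTs.

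The consequence is possible unnecessary de-escalation and extra replacements, not under-detection of toxicity. It should be fixed before the Cohort C run-in opens, but it does not make the design unsound.

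**What to change.** In Sections 3.2.2 and 3.3, add for Cohort C that venetoclax doses withheld under the remission, aplasia or hypoplasia provisions of Section 5.4.1 are not counted as planned doses. The 75% for venetoclax is then taken over doses planned before the hold, and the text should say whether the dose on the day of the hold is included. Leave unchanged the 75% requirement for DS-1594b and azacitidine over the full cycle, and completion of the DLT observation period. This alters only how evaluability is counted, not when venetoclax is held.

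The cost is a sentence or two in two sections and no added subjects; fewer should need replacing. The drawback is that some evaluable subjects will have had less venetoclax. For a hold on Day 17 with that day's dose omitted, 75% of 16 doses is 12, or 12/28 = 43% of the full cycle. Reporting the run-in DLT rate also under the full-cycle 75% count would make this visible.
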